2.2. Baseline Measurement

Baseline measurement is defined as the closest non-missing measurement taken before or at the date of first study agent administration (including time if time is available, with exception of parameters associated with disease-related efficacy assessment such as SPEP, UPEP, kappa, lambda, kappa/lambda ratio, serum calcium, and albumin). If a subject is not treated, the date of randomization will be used.

2.3. Study Agent Dosing Dates

Study agent dosing date is the date on which a subject actually received study agent (partial or complete) and will be recorded in the study agent administration dataset.

The treatment start date for a subject is the date of first daratumumab administration. The last study treatment date is defined as the latest date of non-zero dose of daratumumab administration.

2.4. Imputation for Missing/Partial Dates

Unless specified otherwise, no data imputation will be applied for missing safety and efficacy evaluations. For analysis and reporting purpose, missing or partial dates in adverse event (AE onset date; AE end date), concomitant therapies (start date; end date), SMM diagnosis date, prior therapies (start date; end date) and start date of first antimyeloma therapy will be imputed.

2.4.1. Missing/Partial Adverse Event Onset Date

If the onset date of an adverse event is missing completely or partially, the following imputation rules will be used.

- When month and year are present and the day is missing,
 - If the onset month and year are the same as the month and year of first study treatment, the day of first study treatment or the day-component of the AE end date (possibly imputed) is imputed, whichever is earlier
 - If the onset month and year are not the same as the month and year of first study treatment, then the first day of the month is imputed
- When only a year is present or no components of the onset date are present,
 - If the onset year is the same as the year of first study treatment. If AE end date is available and is prior to first study treatment, the day and month of AE end date are imputed. Otherwise, the day and month of first study treatment are imputed
 - If the onset year is different from the year of first study treatment, the 1st of January is imputed
- If the onset date is completely missing, the date of first study treatment is imputed as the onset date.

No imputation will be done for partial or missing AE onset time.

2.4.2. Missing/Partial Adverse Event End Date

If month and year are present and the day of the month is missing, the last day of the month is imputed.

If only a year is present, the 31st of December is used.

After imputation, if the imputed date is later than the date of death (if available), the date of death will be used as the imputed date instead.

No imputation will be done for partial or missing AE end time.

If AE end date needs imputation, but the AE end time is available, the AE end time will be dropped in the imputed AE end date/time variable.

2.4.3. Partial Concomitant Medication Start/End Date

In case of partially missing concomitant medication start/end dates, the following imputation rules will be applied. If the date is completely missing, no imputation will be performed.

- If only the day is missing, the 15th day of the month will be used
- If both the day and month are missing, the 30th of June will be used

If the medication was taken prior to study start, and the imputed start date is after first treatment date, further adjust of the imputed start date as the day prior to first dosing date; If the medication was taken after study start, and the imputed start date is prior to first dosing date, further adjust the imputed start date as first dosing date. Also adjust the imputed medication end date so that it is on or after first dosing date.

2.4.4. Partial Smoldering Multiple Myeloma Diagnosis Date

For partial date of original smoldering multiple myeloma diagnosis, the following imputation rules will apply:

- If Year is not missing, either Day or Month or both are missing, assume the first day, first month of the year.
- If Year is missing, no imputation will be applied.

2.4.5. Partial Prior Therapy Start/End Date

For partially missing prior smoldering multiple myeloma therapy start/end dates, the following imputation rules will be applied. If the date is completely missing, no imputation will be performed.

- If only the day is missing, the 15th day of the month will be used.
- If both the day and month are missing, the 30th of June will be used.

If the imputed start/end date is after first dosing date, further adjust the imputed start/end date as the day prior to first dosing date.

2.4.6. Partial First Anti-myeloma Therapy Start Date

The imputation rules for missing/partial start dates of subsequent therapies:

If year or month is missing or no components of the start date are present, no imputation will be performed.

If only the day-component is missing, the following steps apply:

- If the month and year of the start date are the same as the month and year of last dosing date, the day of last dosing date or the day-component of the stop date of subsequent anticancer therapy is imputed, whichever is earlier.
- If the start month and year are not the same as the month and year of last dosing date, the first day of the month is imputed.

If after the above imputation are applied, the imputed start date is after the non-imputed end date then re-adjust the start to be the same as the end date.

2.5. Analysis Sets

The following analysis sets are defined in this study.

- Intent-to-treat (ITT)
- Response evaluable
- Safety
- Pharmacokinetic evaluable
- ECG evaluable
- Immune response evaluable

2.5.1. Efficacy Analysis Set(s)

There are two primary efficacy analysis sets:

1. Response evaluable analysis set, defined as subjects who have measurable disease at baseline as per IMWG criteria (serum and urine, serum only, urine only, FLC) and received at least 1 dose of daratumumab treatment. In addition, subjects must have at least 1 post-baseline disease assessment. Analyses of the co-primary efficacy endpoint of complete response will be based on this population.
2. ITT analysis set, defined as subjects who have been randomly assigned to one of the 3 daratumumab schedules based on IWRS. Analyses of the co-primary efficacy endpoint of PD/death rate and secondary efficacy endpoints of progression-free survival (PFS), and overall survival (OS) will be based on this population.

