### 11.1. Subject Information

The main analysis populations are:

- ITT population, defined as randomized subjects
- Safety population, defined as randomized subjects who received at least 1 dose of study agent

The ITT population will be used to summarize the study population and characteristics and efficacy; and the safety population will be used to summarize the safety data.

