### 11.2. Sample Size Determination

Two hypotheses will be tested:

1.  $H_0$ : CR rate  $\leq 15\%$   
 $H_a$ : CR rate  $\geq 35\%$
2.  $H_0$ : PD/death rate  $\geq 0.346/\text{patient-year}$  (median PFS  $< 24$  months)  
 $H_a$ : PD/death rate  $\leq 0.185/\text{patient-year}$  (median PFS  $> 45$  months)

This study will enroll 120 subjects (40/arm) in total. With 40 subjects per arm, each arm will have:

- 90% power to show that the true CR rate is 35% at a one-sided level of 0.05
- 80% power to show that the true PD/death rate is 0.185/patient year at a one-sided level of 0.1

If two or more treatment schedules are deemed to be effective, with 40 subjects per arm this study would have:

- 85% probability of identifying the arm with the higher CR
- 80% probability of identifying the arm with the lower PD/death rate

For the QTc substudy, assuming that the intrasubject standard deviation for change from baseline in QTc ( $\Delta\text{QTc}$ ) is 20 milliseconds and that the true difference in means is 5 milliseconds, a sample size of 25 evaluable subjects (completers) will have 80% power to show that the upper limit of the two-sided 90% confidence interval (1 sided upper 95% confidence interval) for the difference in mean QTc ( $\Delta\text{QTc}$ ) at each timepoint and baseline will be less than 20 milliseconds. To ensure 25 subjects are evaluable, the QTc substudy will enroll approximately 30 subjects.

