### **11.3.1. Primary Efficacy Endpoint**

The primary efficacy endpoints are:

1. CR rate: The number and proportion of subjects who achieve a CR in each arm will be summarized. An exact 90% confidence interval and an exact p-value for rejecting the null hypothesis that the CR rate is 15% will be calculated.
2. PD/death rate: The ratio of subjects with an event (PD or death) to the total follow-up for all subjects will be summarized. A 90% confidence interval and a p-value for rejecting the null hypothesis that the PD/death rate is 0.346 will be calculated.

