1.4. Sample Size Justification

This study will enroll 120 subjects (40/arm) in total. With 40 subjects per arm, each arm will have:

- 90% power to show that the true CR rate is 35% at a one-sided level of 0.05
- 80% power to show that the true PD/death rate is 0.185/patient year at a one-sided level of 0.1

If two or more treatment schedules are deemed to be effective, with 40 subjects per arm this study would have:

- 85% probability of identifying the arm with the higher CR

- 80% probability of identifying the arm with the lower PD/death rate

For the QTc substudy, assuming that the intrasubject standard deviation for change from baseline in QTc (Δ QTc) is 20 milliseconds and that the true difference in means is 5 milliseconds, a sample size of 25 evaluable subjects (completers) will have 80% power to show that the upper limit of the two-sided 90% confidence interval (1 sided upper 95% confidence interval) for the difference in mean QTc (Δ QTc) at each timepoint and baseline will be less than 20 milliseconds. To ensure 25 subjects are evaluable, the QTc substudy will enroll approximately 30 subjects.

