5. EFFICACY

5.1. Analysis Specifications

5.1.1. Level of Significance

For the co-primary endpoint of CR rate a 1-sided alpha of 0.05 will be used. For the co-primary endpoint of PD/death rate a 1-sided alpha of 0.1 will be used. No adjustments for multiplicity will be made.

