5.2.2. Analysis Methods

5.2.2.1. Complete Response

The number and percentage of subjects who achieve a complete response including 90% exact CI will be calculated for each treatment group based on response evaluable population. The exact p-value to test the hypothesis, H_0 : CR rate $\leq 15\%$ will also be calculated.

A similar analysis based on complete response based on investigator assessment will also be conducted.

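### The SAP tests the co-primary CR rate only in a response-evaluable set, although the protocol assigns efficacy to ITT, and no ITT analysis of CR is planned

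*SAP*

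**What the plan says.** Protocol 11.1 names ITT (all randomized subjects) and Safety as its main populations and states: "The ITT population will be used to summarize the study population and characteristics and efficacy". Protocol 9.2.2.1 and 11.3.1 treat CR rate as a proportion of the subjects in each arm, with no evaluability condition. The planned analysis is: "An exact 90% confidence interval and an exact p-value for rejecting the null hypothesis that the CR rate is 15% will be calculated".

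SAP 2.5.1 introduces a response-evaluable set with three conditions: measurable disease at baseline, at least one dose of daratumumab, and a later disease assessment ("In addition, subjects must have at least 1 post-baseline disease assessment"). It then says: "Analyses of the co-primary efficacy endpoint of complete response will be based on this population". SAP 5.2.2.1 repeats this: the CR count, percentage and exact interval "will be calculated for each treatment group based on response evaluable population". The other co-primary endpoint, PD/death rate, stays on ITT.

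The only further CR analysis in SAP 5.2.2.1 uses investigator assessment. SAP 5.1.2 leaves missing efficacy values unimputed, and Protocol 10.4 does not replace withdrawn subjects. On size and level, the SAP says "This study will enroll 120 subjects (40/arm) in total" and "For the co-primary endpoint of CR rate a 1-sided alpha of 0.05 will be used". Both documents claim, per arm, "90% power to show that the true CR rate is 35% at a one-sided level of 0.05", without any allowance for non-evaluable subjects.

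**The concern.** The two documents name different denominators for a co-primary test, and the SAP gives no reason for the change. Two of its three conditions are met or missed after randomization. Under the notes to Protocol Table 4, a response needs two consecutive assessments, so a subject who was never dosed or never assessed cannot have a documented CR. Taking such subjects out leaves the numerator alone and shrinks the denominator. The error therefore runs in one direction, and there is no ITT result to set beside it.

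Protocol 11.3 and 11.9 use this analysis to choose a dose and schedule and to decide on Phase 3. Near the rejection boundary, one or two subjects settle the answer.

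**Working it through.** **Inputs.** Null CR rate 0.15, alternative 0.35, one-sided level 0.05, 40 per arm (Protocol 11.2; SAP 1.3, 1.4, 5.1.1); exact test (Protocol 11.3.1; SAP 5.2.2.1). The number non-evaluable per arm, k, is in neither document. It is an assumption here, shown over a range.

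**The plan's own figure (90% power).** The normal approximation with continuity correction gives

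Φ[(0.35 − 0.15 − 0.5/40 − 1.645·√(0.15·0.85/40)) / √(0.35·0.65/40)] = Φ[(0.1875 − 0.0929)/0.0754] = 89.5%.

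Without the correction it is 92.2%. So 90% can be reproduced approximately. For the exact test that is planned:

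- P(X ≥ 10 | 40, 0.15) = 0.0672, which exceeds 0.05.
- P(X ≥ 11 | 40, 0.15) = 0.0299, so the rule is to reject at 11 or more of 40.
- P(X ≥ 11 | 40, 0.35) = 0.8785, so the power is 87.9%.

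**One set of data, different denominators.** With 10 CRs, p = P(X ≥ 10 | n, 0.15):

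- n = 40: p = 0.067, not rejected
- n = 39: p = 0.058, not rejected
- n = 38: p = 0.0495, rejected

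**Type I error against the ITT null.** Hold the ITT CR rate at 15%, which is 6 expected CRs in 40. Let k non-responders be excluded. The CR rate among the evaluable is then 6/(40 − k). Apply the exact rule for n = 40 − k:

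| k excluded | n | Reject at | Level against 15% in the evaluable set | Evaluable CR rate | Error against ITT null |
|---|---|---|---|---|---|
| 0 | 40 | 11 | 2.99% | 15.0% | 2.99% |
| 1 | 39 | 11 | 2.50% | 15.4% | 2.96% |
| 2 | 38 | 10 | 4.95% | 15.8% | 6.6% |
| 4 | 36 | 10 | 3.51% | 16.7% | 6.5% |
| 6 | 34 | 10 | 2.40% | 17.6% | 6.4% |
| 7 | 33 | 9 | 4.95% | 18.2% | 13.1% |

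The jumps come from the critical value falling from 11 to 10 and then to 9.

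**Random rather than fixed exclusions.** Suppose each subject is excluded with probability q, always as a non-responder. The error against the ITT null is 3.8% at q = 2.5%, 4.99% at 5%, 6.7% at 10% and 10.1% at 17.5%. It crosses 5% at an average exclusion rate of about 5%.

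**With ITT as the denominator.** The rule stays at 11 of 40 and the error at 2.99%, whatever the number non-evaluable.

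**The case against.** Protocol section 11 leaves specific details to the SAP, and a CR rate among subjects who could be assessed is a legitimate measure of activity. For that rate the exact test keeps its level at every n in the table. This is also a Phase 2 screen with openly liberal error rates and no multiplicity adjustment. Early loss may be rare: treatment starts within 5 days of randomization and the first disease assessment is at Week 5.

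Much of this stands, and it rules out several stronger readings.

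- *The CR test exceeds its 5% level.* This does not follow as a matter of course. The exact test spends only 2.99% at n = 40, so with 0 or 1 exclusion the error stays near 3% even against the ITT null. The excess needs 2 or more exclusions, all non-responders, and the documents give no rate.
- *Everyone excluded is a certain non-responder.* This holds for undosed and unassessed subjects. It does not hold for those without measurable baseline disease, which is a pre-randomization feature; the notes to Table 4 allow CR to be coded whether or not baseline disease was measurable.
- *Exclusions erode power.* That requires holding the evaluable CR rate at 35%. On the basis used for the type I error (ITT rate fixed, excluded subjects non-responders), power at 34 to 36 evaluable is about 94%.
- *The randomized comparison of schedules is broken.* Each arm is tested separately against 15%, no between-arm CR test is planned, and weekly dosing is identical in all arms throughout Cycle 1. Knowledge of assignment in an open-label trial could still affect early loss, but the documents give no evidence of it.
- *The 90% power is an error.* The method behind it is not stated, and 89.5% is close. The gap to the exact value is about 2 points.

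What the objection does not answer is why a co-primary test leaves the protocol's population without explanation and without an ITT counterpart. Changing the population is more than a detail.

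**Conclusion.** The point holds as a conflict between protocol and SAP on the population for a co-primary test. The bias has a known direction, its size is unknown, and no ITT analysis is planned that would reveal it. If the ITT CR rate is 15% and the excluded subjects are non-responders, the one-sided error against the ITT null is about 3% with 0 or 1 of 40 excluded, 6.4–6.6% with 2 to 6, and about 13% with 7. A result of 10 CRs changes from non-significant to significant once two subjects are removed. These figures rest on an assumed number of exclusions and on reading the 15% null as a rate among all randomized subjects, which is what Protocol 11.1 implies.

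The power figure is a secondary matter: about 88% for the exact test as planned.

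**What to change.** In SAP 2.5.1 and 5.2.2.1, make ITT the primary set for CR. Count any subject without a documented CR as a non-CR, including those never dosed or never assessed. Subjects without measurable baseline disease should enter with their observed response under Protocol Table 4 and should not be set to failure. Keep the response-evaluable analysis as supportive, and report the number excluded per arm with reasons. Align ORR in SAP 5.3.2.2 in the same way.

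In Protocol 11.2 and SAP 1.4, state the power of the exact test at n = 40 as about 88%, with rejection at 11 or more CRs and an attained one-sided level of 0.030.

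The cost is wording only, with no new data. The CR estimate will be slightly lower wherever subjects are non-evaluable, and the stated power falls by about 2 points.

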2.5.2. Safety Analysis Set

The safety analysis set is defined as subjects who have received at least 1 administration of daratumumab (partial or complete). This population will be used for all safety analyses. The safety analyses grouping will be according to treatment actually received.

2.5.3. Pharmacokinetics Analysis Set

The pharmacokinetics analysis set is defined as subjects who received at least 1 administration of daratumumab and have at least 1 pharmacokinetic sample concentration value after the first infusion. All pharmacokinetics analyses are based on the pharmacokinetic evaluable population.

2.5.4. Immune Response Analysis Set

The immune response analysis set is defined as subjects who have at least 1 immunogenicity sample obtained after their first daratumumab administration.

2.6. Definition of Subgroups

The following pre-specified subgroups will be used to analyze some of the efficacy endpoints

Table 1: Subgroup Analyses for Efficacy Endpoints		
Subgroup	Definition	Analysis Type
Sex	Male, Female	E
Age	<65, 65 - < 75 years, ≥75 years	E
Race	White, Others	E
ECOG performance score	0, 1	E
E: efficacy (PFS and ORR)		

3. INTERIM ANALYSIS

There will be an interim analysis 6 months after the last subject is randomized. The objective of this interim analysis is to assess the primary endpoint of CR to help guide future development of daratumumab in SMM. For the second primary endpoint of PD/death rate per patient-years descriptive statistics will be provided but a formal statistical analysis will not be conducted at this interim analysis. All available data at the time of this data cutoff may be included in the interim analysis.

4. SUBJECT INFORMATION

4.1. Demographics and Baseline Characteristics

Unless specified otherwise, all demographic and baseline characteristics variables will be summarized using the ITT analysis set.

Subject enrollment of the study will be summarized for each treatment group according to country. The number of subjects by study treatment assigned versus study treatment received will be tabulated. A list of subject's randomization information will be provided. Subjects who did not meet study inclusion/exclusion criteria will be listed.

Subject demographic variables: age (<65 years, 65- < 75 years, and ≥ 75 years), sex, race, height (cm) and weight (kg) will be summarized by treatment group. Baseline disease characteristics including type of smoldering multiple myeloma, bone marrow plasma cell (%), serum free light chain ratio, and Eastern Cooperative Oncology Group (ECOG) performance status will be summarized and tabulated by treatment group. Time from first date of initial diagnosis of smoldering myeloma to randomization will be summarized by descriptive statistics. Additionally, the number of subjects who meet intermediate or high-risk MM criteria specified in the protocol will be reported for each treatment group, respectively.

Baseline skeletal survey and magnetic resonance imaging test results based on investigator assessment will be tabulated. Serum and urine M-protein and quantitative immunoglobulin (IgG, IgA, IgM, IgD, and IgE) will be summarized and presented for each treatment group.

A summary of hematology and chemistry laboratory values at baseline by descriptive statistics and frequency will be provided. The categorization for each laboratory parameter is based on the threshold specified in the inclusion criteria.

Medical history collected at baseline or screening visit will be summarized by system-organ class and preferred term for each treatment group and overall.

The interpretation of 12-ECG test will be classified as 3 categories: within normal limits; abnormal, clinically insignificant; and abnormal, clinically significant, the number and percentage of subjects in each category at baseline will be summarized by treatment group.

For subjects who had either Fluorescence in situ hybridization (FISH) or karyotype testing done, cytogenetic abnormality is classified into 2 categories: high-risk and standard-risk. High-risk abnormality is defined as:

- By FISH: t (4; 14), t (14; 16), amp1q21 and 17p deletion.
- By karyotype: t (4; 14) and 17p deletion.

Otherwise, known cytogenetic abnormality has standard-risk.

Subjects meeting the high-risk cytogenetic abnormality criteria will be summarized by the cytogenetic type. In addition, cytogenetic testing methods based on bone marrow investigation will be summarized by the type of analyses performed. The number and percentage of subjects with numerical/ structural changes will be reported for subjects with karyotype testing. For subjects with FISH testing, the number and percentage of subjects with interphase/metaphase FISH will be reported.

4.2. Disposition Information

The number of subjects who are randomized to each treatment group will be summarized. The number and percentage of subjects who are randomized but not treated will be reported. For subjects in safety analysis set, the number and percentage of subjects who discontinued treatment including reasons for discontinuation will be summarized by treatment group. Similar summaries will be presented for subjects who discontinued study including reasons for discontinuation.

